8.2 Efficacy Assessments

8.2.1 Caries Examination

Two examiners will be trained and calibrated according to National Institute of Dental and Craniofacial Research Early Childhood Caries Collaborative criteria, which are based on the World Health Organization caries classification system. The children will be visually examined using a mouth mirror and artificial light. No explorers will be used. The outcome will be assessed by visual examination by two trained and calibrated examiners.

8.3 Safety Assessments

Adverse events, including frequency and severity, and perceived relationship to the investigational product, will be compared between the treatment groups.

8.3.1. General Health (Medical History and Physical Examination)

The subject's general health status at enrollment will be assessed by medical history using the parent or legal guardian as the informant.

The Study Site Coordinator will rule out a history of thyroid disease and iodine allergy (e.g., allergy to seafood).

All concomitant medications taken by the subject will be recorded at the time of consent and updated at each follow-up study visit (including all prescription and over-the-counter medications, vitamins, and nutritional supplements taken within the past three months).

9. Assessment of Safety

9.1 Specification of Safety Parameters

- Adverse events

9.2 Methods and Timing for Assessing, Recording, and Analyzing Safety Parameters

Adverse events will be recorded at each contact with the teacher or parent.

Adverse events will be reviewed on a monthly basis by the Medical Monitor ([name]); serious adverse events and other protocol-specified reportable events will be assessed in real time by the Principal Investigator ([name]) and Site Director ([name]).

9.3 Adverse Events

An adverse event (AE) is any untoward medical occurrence associated with the use of a drug in humans, whether or not considered drug related. An AE can therefore be any unfavorable and unintended sign, symptom, or disease temporally associated with any use of a drug, whether or not related to the drug. An adverse event can arise from any use of the drug (e.g., off-label use, use in combination with another drug) and from any route of administration, formulation, or dose. This excludes minor fluctuations in signs or symptoms of the disease under study, but includes significant worsening of the disease. It also includes any apparently unrelated illness and any accident that occurs during participation in the study.

Some examples of adverse events are:

- Development of an illness during the study.
- Development of symptoms which may or may not be related to the use of a concomitant medication or investigational product.

All adverse events, whether observed by the Principal Investigator, elicited from or volunteered by the subject, subject's teacher or parent/guardian, should be recorded on the Adverse Event Log. This reporting will include a brief description of the event, the date of onset, the date of resolution, the duration and type of event, the severity, contributing factors, and any action taken with respect to the investigational product.

AEs occurring after informed consent is obtained but prior to randomization will be recorded as medical history, unless possibly related to a study procedure, in which case they will be recorded as adverse events in the case report form. New adverse events will be captured and reported on the AE log until 30 days following the last treatment or premature withdrawal, whichever comes first.

9.4 Expected Adverse Reactions

Risks from povidone iodine include rash and swelling at the site of application. Iodine can cause thyroid gland problems.

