A phase 1 study of the safety of the new varnish was conducted in 12 healthy children with an average age of 47.6 months (WIRB PRO NUM: 20160539). No child evidenced any intra oral erythema or secondary changes as a consequence of the varnish application either immediately or within 24-48 hours post application. Neither were there any adverse effects. The FDA has reviewed the previous safety work and this protocol and issued IND 128835 for this work. The basic dental varnish formula was previously cleared by the FDA as a medical device and is currently on the market. To our knowledge there have been no adverse event reports on this varnish and it has never been withdrawn from the market. Povidone iodine is widely used in children in medicine. It has been used for intraoral application for many years without problems. Dental NaF varnish and povidone iodine have been applied sequentially at the same patient visit by clinicians for some time and two cohort studies have been published with no reports of harms.

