6.2 Dosage, Preparation and Administration of Study Investigational Products

Advantage Anti-Cavity Varnish and Control Varnish

A maximum of 0.2 mL will be applied to the teeth with a dental brush.

Test or control varnish will be applied topically following baseline examination and at each 3 to 4-month intervals.

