7.2 First Treatment Visit

- A study assistant will consult the student list and apply the assigned treatment.
- The study assistant will administer the Facial Images Scale, immediately following the varnish treatment.

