7.4 Follow-Up Contacts

The subject's teacher will be contacted 48 hours following treatment. If the child is not attending or the teacher knows of a problem, the parent will be contacted to determine if there is a reportable AE. The medical monitor will assign causality. No treatments will be done on Fridays to avoid having to make home visits in order to obtain the basic AE information on the weekend.

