7.6 Unscheduled Visit

An unscheduled visit may be performed at any time during the study at the subject's request or as deemed necessary by the Principal Investigator. The date and reason for the unscheduled visit will be recorded in the subject's source documentation.

Activities to be completed include:

- The Examiner will conduct the Oral Soft Tissue exam
- The Examiner will conduct the caries exam
- The assistant will record concomitant medication use.
- The assistant will review and record on the AE Follow-Up Log the status of adverse events that are unresolved at the time of the unscheduled visit.

8. Assessments

[figure not shown]

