9.6 Reporting Procedures

9.6.1 Reportable Events

The following incidents will be considered reportable events and will be reported to the Principal Investigator within 24 hours of the site's awareness of the event.

- Serious Adverse Event
- Emergency Treatment Disclosure
- Post-Treatment Adverse Events*, including
 - Nausea
 - Not eating
 - Vomiting
 - Difficulty swallowing or breathing
 - Swelling around the lips or skin on the face
 - Itchiness around the lips or skin of the face
 - Hives or rash

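### Swelling at the application site is an expected reaction, but no listed procedure inspects the oral soft tissue within 48 hours of an application, so oral reactions are likely to be under-counted

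*Combined protocol and SAP*

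**What the plan says.** - **Expected reaction.** Protocol 9.4: "Risks from povidone iodine include rash and swelling at the site of application". Section 2.2.1 states the same risk.
- **Where and how often the product is applied.** Section 6.2: "A maximum of 0.2 mL will be applied to the teeth with a dental brush", and "Test or control varnish will be applied topically following baseline examination and at each 3 to 4-month intervals".
- **First treatment visit (7.2).** Two steps are listed: applying the assigned varnish, and then "The study assistant will administer the Facial Images Scale, immediately following the varnish treatment".
- **Visits 2 to 8 (7.3).** A dental and oral examination is scheduled at visits 4 and 8 and is listed ahead of that visit's application. Adverse events are reviewed at every one of these visits.
- **After each treatment (7.4).** "The subject's teacher will be contacted 48 hours following treatment". The parent is contacted only if the child is absent or the teacher is aware of a problem.
- **Soft tissue exam.** "The Examiner will conduct the Oral Soft Tissue exam" appears for unscheduled visits (7.6) and for premature withdrawal (7.5), and for no routine visit.
- **Reportable post-treatment events (9.6.1).** The swelling item reads "Swelling around the lips or skin on the face", and itchiness is placed at the same sites. The list also has nausea, vomiting, not eating, difficulty swallowing or breathing, and hives or rash with no site given.
- **Phase 1 (2.1).** In 12 children, "No child evidenced any intra oral erythema or secondary changes as a consequence of the varnish application", assessed both immediately and at 24 to 48 hours.
- **Analysis (11.3.2).** For each adverse event, the arms are compared on the occurrence of at least one event with Fisher's exact test.

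**The concern.** Secondary objective (b) in 3.1 is to document the safety of the test varnish, adverse event occurrence is a secondary outcome (3.2.2), and 11.1 hypothesises no difference in adverse event frequency. Iodine is the only intended active difference between the arms (6.1.2), and a local reaction to iodine is the expected harm. Such a reaction may be mild, short-lived and out of sight, so it will be recorded reliably only if someone looks or asks within a day or two.

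A low count of oral reactions could then mean either good tolerance or incomplete observation, and the report could not tell them apart. The children who did receive a soft tissue exam would be those who complained or withdrew. The missing observation also works in favour of the stated safety hypothesis, because fewer recorded events in both arms make a difference harder to see.

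**Working it through.** The plan gives no figure for the local reaction rate, so there is nothing of its own to reproduce. The check compares the procedures with the reaction window and then illustrates what partial capture would do.

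**Step 1: each opportunity to observe, set against the window (immediately to 48 hours).**

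| Procedure | Section | Timing relative to the last application | Looks at oral soft tissue? |
|---|---|---|---|
| Facial Image Scale | 7.2, 8.1 | Immediately after | No; records the child's response |
| Teacher contact | 7.4 | 48 hours | No |
| Parent contact | 7.4 | After 48 hours, only if triggered | No; report only |
| Adverse event review, visits 2 to 8 | 7.3 | If it covers the preceding interval, 3 to 4 months | No; report only |
| Dental and oral examination, visits 4 and 8 | 7.3 | About 3 to 4 months, as it is listed before that visit's application | Yes, but outside the window |
| Oral Soft Tissue exam | 7.5, 7.6 | Any time, selected children | Yes, not routine |

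No row is both inside the window and a routine look in the mouth.

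**Step 2: the 9.6.1 list.** No item names swelling, redness or sores inside the mouth. Not eating and difficulty swallowing could signal a marked oral reaction. A child with mildly swollen gums who attends school and eats matches none of the items.

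**Step 3: what phase 1 leaves open.** The one-sided 95% upper limit for zero events in n children is 1 − 0.05^(1/n). For n = 12 this is 1 − 0.05^(1/12) = 22.1%. Phase 1 therefore does not settle the rate.

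**Step 4: effect of partial capture (assumed values).** Let p be the true proportion of test-arm children with an oral reaction and s the share of those that get recorded. The documents give neither. The arm size is 140 (280/2, from 11.2) or 300 (600/2, from 5.1).

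- Expected recorded cases = n·p·s
- Chance of recording at least one = 1 − (1 − p·s)^n
- If none is recorded, the upper limit for p is [1 − 0.05^(1/n)]/s

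With p = 2%:

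| s | n = 140: expected cases | chance of ≥1 | limit if zero recorded | n = 300: expected cases | chance of ≥1 | limit if zero recorded |
|---|---|---|---|---|---|---|
| 100% | 2.8 | 94% | 2.1% | 6.0 | 99.8% | 1.0% |
| 50% | 1.4 | 76% | 4.2% | 3.0 | 95% | 2.0% |
| 25% | 0.7 | 50% | 8.5% | 1.5 | 78% | 4.0% |
| 10% | 0.28 | 24% | 21.2% | 0.6 | 45% | 9.9% |

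Over a range of p with n = 140, going from s = 100% to s = 25%, the chance of at least one recorded case falls from 76% to 30% at p = 1%, and from 99.9% to 83% at p = 5%. At s = 10% and n = 140, a zero count would bound the rate at 21.2%, hardly tighter than the 22.1% from 12 children in phase 1.

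**Step 5: the arm comparison.** If s is the same in both arms, as double-blinding makes plausible, the expected recorded difference is s × (p_test − p_control). The ratio of rates is unchanged in expectation, but the difference shrinks by the factor s and the counts are smaller, so Fisher's test is less able to show a difference.

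**The case against.** The strongest case on the other side has four parts.

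1. **Capture is open-ended.** Section 9.3 records every adverse event, whether observed, elicited or volunteered. Section 9.2 records events at each teacher or parent contact, and 9.5.2 adds an assessment of clinical features. Visits 2 to 8 include an adverse event review. This stands, and it is why the defect is under-counting. A reader might infer that the trial cannot measure its expected local reaction at all. The documents do not support that, because detection would be nil only if no reaction were ever reported.
2. **Mouths are examined, and the list is broader than the face.** A reader might infer that no scheduled procedure ever looks in the mouth after an application, or that 9.6.1 covers only lips and facial skin. Neither is right. Section 7.3 schedules oral examinations at visits 4 and 8, so the gap is one of timing. Section 9.6.1 includes feeding, swallowing and unsited rash items; only swelling and itchiness are tied to lips and face.
3. **The method may be described elsewhere.** Sections 14.2 and 14.3 name expected adverse reactions among the data to be collected. The section 8 figure is not shown, the footnote to the starred item in 9.6.1 is not visible, and the worksheets (12.2) and safety monitoring plan (14.4) are separate documents. This stands as a limit on the finding, which concerns the procedures listed in the visible text.
4. **The oral location is an inference.** In 2.2.1 the risk statement follows a remark about use on skin, and 2.1 reports many years of intraoral use without problems. The protocol does not say that it expects gum or mucosal swelling. But 6.2 puts the product on the teeth, and phase 1 looked specifically inside the mouth, so reading the application site as oral is reasonable.

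**Conclusion.** The concern holds as a matter of ascertainment. On the listed procedures, oral reactions in the immediate to 48-hour window are captured only passively. They are likely to be under-counted in both arms, and the comparison in 11.3.2 is pulled toward no difference.

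The size of the under-count cannot be derived from the documents, since neither the reaction rate nor the reporting share is given. The table in the working shows a range under assumed values; it is not an estimate. The zero-event limits (22.1%, 2.1% and 1.0%) show what full observation could establish. A reader might take them as the number of reactions missed, but they do not measure that.

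The conclusion rests on three assumptions: that a local reaction would arise mainly inside the mouth, that the order of steps in 7.3 is the order of conduct, and that the material not visible adds no inspection after application. The change is worth making because it is cheap and bears directly on secondary objective (b).

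**What to change.** - **9.6.1:** add swelling, redness or sores inside the mouth to the post-treatment events.
- **7.4:** have the 48-hour contact ask specifically about a sore or swollen mouth.
- **7.2 and 7.3:** have the assistant who applies the varnish record the oral soft tissue as none or present just before and just after each application. The before look separates existing lesions from new ones. Section 5.7 keeps this person separate from the caries examiner, so masking of the primary outcome is unaffected.
- **11.3.2:** report the proportion of children with an oral reaction by arm, with a confidence interval, alongside Fisher's test. State how many children were actually observed after application.

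If the section 8 schedule, the 9.6.1 footnote or the worksheets already require such a check, a cross-reference in 7.2, 7.3 and 7.4 would be enough for that part.

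**Cost:** a brief look by staff already working in the child's mouth, one line on the form, one question and some wording; no added visits or staff. **Downside:** an assistant's look is cruder than an examiner's exam and catches only immediate reactions. Later ones would still depend on the 48-hour question.

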9.5 Serious Adverse Events

A serious adverse drug event is defined as any adverse event that results in any of the following outcomes:

- death
- a life-threatening adverse event
- inpatient hospitalization or prolongation of existing hospitalization
- a persistent or significant incapacity; or substantial disruption of the ability to conduct normal life functions
- [a congenital anomaly/birth defect – noted as not applicable in this population]

An important medical event that may not result in death, be life-threatening, or require hospitalization may be considered serious when, based upon appropriate medical judgment, the event may jeopardize the subject and may require medical or surgical intervention to prevent one of the outcomes listed in this definition. Examples of such medical events include (but are not limited to) allergic bronchospasm requiring intensive treatment in an emergency room or at home, or blood dyscrasias or convulsions that do not result in inpatient hospitalization.

This category also includes any event the Principal Investigator judges to be serious or that would suggest a significant hazard, contraindication, side effect or precaution. Any adverse event or suspected adverse reaction is considered "life threatening" if, in the view of either the Principal Investigator or sponsor, its occurrence places the patient or subject at

immediate risk of death. It does not include an adverse event or suspected adverse reaction that, had it occurred in a more severe form, might have caused death.

Reports of serious adverse events require immediate notification (within 24 hours of the site's awareness) to the Principal Investigator and Sponsor whether or not the Study Site Coordinator believes that the event is related to investigational product or is expected.

9.5.1 Unanticipated Problems

The Principal Investigator must conform to the adverse event reporting timelines, formats and requirements of the various entities to which he is responsible, but at a minimum those events that must be reported are those that are:

- related to study participation,
- unexpected, and
- serious or involve risks to subjects or others

9.5.2 Procedures to be Followed in the Event of Abnormal Clinical Findings

At each parent or teacher contact the site study staff will assess adverse events by recording all reports by the subject's parent/guardian or teacher and by assessment of clinical features.

An unscheduled visit may be performed at any time during the study as deemed necessary by the Principal Investigator. The Site Director will inform the subject's parent/guardian when medical care is needed for adverse events of which the Principal Investigator becomes aware (e.g., illness) and may refer the subject back to the PCP for further work-up. The Principal Investigator may determine that the subject should be withdrawn from the study treatment.

9.6 Reporting Procedures

9.6.1 Reportable Events

The following incidents will be considered reportable events and will be reported to the Principal Investigator within 24 hours of the site's awareness of the event.

- Serious Adverse Event
- Emergency Treatment Disclosure
- Post-Treatment Adverse Events*, including
 - Nausea
 - Not eating
 - Vomiting
 - Difficulty swallowing or breathing
 - Swelling around the lips or skin on the face
 - Itchiness around the lips or skin of the face
 - Hives or rash

9.6.2 Serious Adverse Events

Within 24 hours of the site's awareness of the serious adverse event (SAE), the site will report the SAE to the Principal Investigator and provide subject identification and a brief description of the event, including the Medical Monitor's assessment of causality (unrelated, unlikely related, possibly related, probably related, or definitely related to the study drug).

Within 24 hours of the telephone report, the site will update the AE log to ensure that the concomitant medication log is current, and enter the SAE report. This report will include: documentation that serious adverse event criteria have been met; a detailed description of the event and other relevant information; the current status of the experience; if the subject has died, the date of death and autopsy report, if available; and the Medical Monitor's current opinion of the relationship between the event and the investigational treatment.

9.6.3 Adverse Event Causality Definitions

For each adverse event, the relationship to the study drug (Medical Monitor's attribution of causality) must be recorded as one of the following on the Adverse Event Log:

TERM	DEFINITION	CLARIFICATION
Unrelated	No possible relationship	The temporal relationship between drug exposure and the adverse event onset/course is unreasonable or incompatible, or a causal relationship to study drug is implausible.
	Not reasonably related, although a causal relationship cannot be ruled out	While the temporal relationship between drug exposure and the adverse event onset/course does not preclude causality, there is a clear alternate cause that is more likely to have caused the adverse event than the study drug.
Possible	Causal relationship is uncertain	The temporal relationship between drug exposure and the adverse event onset/course is reasonable or unknown, dechallenge or rechallenge information is either unknown or equivocal, and while other potential causes may not exist, a causal relationship to the study drug does not appear probable.
Probable	High degree of certainty for causal relationship	The temporal relationship between drug exposure and the adverse event onset/course is reasonable. There is a clinically compatible response to dechallenge (rechallenge is not required), and other causes have been eliminated or are unlikely.
Definite	Causal relationship is certain	The temporal relationship between drug exposure and the adverse event onset/course is reasonable, there is a clinically compatible response to dechallenge, other causes have been eliminated, and the event must be definitive pharmacologically or phenomenologically, using a satisfactory rechallenge procedure if necessary.

9.6.4 Adverse Event Severity Definitions

The severity of each adverse event must be recorded as one of the following on the Adverse Event Log:

MILD	No limitation of usual activities
MODERATE	Some limitation of usual activities
SEVERE	Inability to carry out usual activities

9.7 Responsibilities of Investigator/Sponsor/ for Reporting Serious Adverse Events

Serious adverse events occurring after informed consent is obtained but prior to randomization will be recorded as medical history, unless possibly related to a study procedure, in which case they will be reported as SAEs to the Medical Monitor within 24 hours of the site's awareness.

9.7.1 Regulatory Reporting for Studies Conducted Under an IND

The Principal Investigator will comply with the Western IRB regulations regarding the reporting of adverse events.

The Sponsor will report events that are serious, unexpected and that are associated with the study drug (SUSAR) to the Food and Drug Administration (FDA) within the required timelines as specified in 21 CFR Part 312.32; fatal and life-threatening events within 7 calendar days (by phone or fax) and all other SAEs in writing within 15 calendar days. All serious events designated as "not associated" with study product(s) will be reported to the FDA at least annually in a summary format.

